## Protocol

---

I. Research Project Title:

ACTION PAC: Adolescents Committed to Improvement of Nutrition & Physical Activity

NCT number: NCT02502383

Date: January 26, 2016

II. Investigator's Name, Degree, Title, and Department: [name], MPH, Associate Professor, Department of Pediatrics

III. Hypothesis or Study Goals (questions hoped to be answered by study):

Specifically, our goals are to 1) prevent the development of overweight and obesity among students with BMI <85th percentile, 2) reduce BMI z score by 0.16 (change documented in a high intensity obesity intervention that produced clinical improvements in insulin resistance) in students with BMI ≥85th percentile, 3) reduce insulin resistance (as measured by the homeostasis model assessment) in students with BMI ≥85th percentile, and 4) obtain participants' feedback on their experience with school-based BMI screening and weight management to guide future dissemination efforts and studies. To achieve these goals, we aim to:

- 1) Evaluate motivational interviewing (MI) as a method to prevent overweight/obesity in students with BMI <85th percentile.
  - a. Hypothesis 1a -- Intervention schools (where parents are sent annual BMI results and students receive MI-based discussion of BMI results, healthful eating and physical activity) will have a lower incidence of overweight/obesity among their students compared with comparison schools (where parents are sent annual BMI results but students do not receive MI-based discussion) after two years.
  - b. Hypothesis 1b -- Intervention schools will evidence greater mean improvements in physical activity and dietary intake (e.g., decreased consumption of sugar-sweetened beverages, decreased fat intake, and increased consumption of fruits, vegetables and whole grains) compared with comparison schools after two years.
- 2) Evaluate the SBHC weight management program (ACTION) that utilizes MI for treatment of overweight/obesity for intervention school students with BMI ≥85th percentile.
  - a. Hypothesis 2 -- Compared with comparison school students with BMI ≥85th percentile, students receiving ACTION will have greater reduction in BMI z score and insulin resistance after two years.
- 3) Evaluate student and parent feedback at the end of the intervention trial about their experience with school-based BMI screening and weight management to inform future dissemination efforts and studies.

IV. Background:

- i) Describe relationship of proposed study to previous investigations in the field, summarize those previous studies, including previous human, laboratory, and animal studies (describe existing knowledge).

High prevalence of obesity and metabolic syndrome: Since 1980, the prevalence of childhood obesity in the U.S. has tripled to 17%, affecting 12.5 million school-age children and adolescents. Associated with this epidemic is the rising prevalence of metabolic (or insulin resistance) syndrome among adolescents, typically described as a clustering of five cardiometabolic risk factors that includes central adiposity, elevated blood pressure, hypertriglyceridemia, low HDL-cholesterol, and impaired glucose metabolism. Longitudinal studies show that children and adolescents with at least three of these metabolic derangements are more likely to suffer cardiovascular disease 25 years later and to develop type 2 diabetes. Recent data reveal that the prevalence of metabolic syndrome in all U.S. teens varies from 2.0% to 9.4%; however, in obese teens, prevalence escalates from 12.4% to 44.2%. Therefore, as recommended by the American Heart Association, to prevent the development of metabolic syndrome, overweight and obese adolescents need lifestyle modification to assist with weight loss, and normal weight youth should be encouraged to adopt healthier lifestyle habits to maintain their weight.

Racial and ethnic disparities of obesity and metabolic syndrome: There are large disparities in overweight (defined in children and adolescents as BMI 85th-94th percentile) and obesity (BMI ≥95th percentile) between demographic groups. Adolescents from several minority groups have the greatest increases in adiposity compared to their counterparts. Nationally, Hispanic adolescents experience significantly higher BMI rates than non-Hispanic Whites. In New Mexico, American Indian youth have the highest rate of obesity (17.8%), double that of White youth (8.7%); African American (13.5%) and Hispanic (12.8%) youth also have high rates --

about one-third higher than White youth. More concerning is that obese youth gain more body fat over time, especially more central fat as indicated by waist circumference. This increase is concerning because it is a component of the metabolic syndrome and a direct predictor of cardiovascular disease and type 2 diabetes. In a study of Hispanic youth in Los Angeles, 90% of overweight Hispanic children with a family history for type 2 diabetes had at least one feature of metabolic syndrome with 30% already meeting clinical criteria for metabolic syndrome.

High economic costs of obesity and metabolic syndrome: The economic costs of childhood obesity compound the consequences of the epidemic. Annual prescription drug, emergency room and outpatient costs amount to \$14 billion and inpatient costs total \$238 million. Even greater cost is incurred when obese children become obese adults. An estimated \$147 billion is expended to treat obese adults annually. A study that investigated health care utilization and costs associated with metabolic syndrome in three health plans in Seattle found that average annual total costs for patients with metabolic syndrome compared to those without metabolic syndrome differed by a factor of 1.6 (\$5,732 vs. \$3,581).

Prediabetes and type 2 diabetes in adolescents: In a recent National Health and Nutrition Examination Survey, nearly one in four adolescents, ages 12-19 years, had prediabetes or type 2 diabetes as defined by a fasting plasma glucose >99 mg/dL. This is a sharp increase from 9% in 1999-2000 to 23% in 2007-2008. As type 2 diabetes progresses more rapidly in children and adolescents than in adults and is harder to treat ( $\geq 50\%$  treatment failure rate), it is imperative to prevent adolescents from developing the disease. People with prediabetes can prevent developing type 2 diabetes with modest weight loss and exercise. Therefore, obesity treatment through lifestyle modification is possible for reducing long-term negative outcomes, and is an approach that is urgently needed for adolescents.

Limited healthcare access for adolescents: Adolescents averaged 1.9 clinical visits/year, lower than any other pediatric age-group. School-based health centers (SBHCs) offer a unique and important method to expand healthcare access for all adolescents, including those who do not have adequate health insurance. SBHCs provide preventive and primary health care services to all students on school campuses, with a particular focus on assisting uninsured and underserved youth. This healthcare model has demonstrated utility in intervening with public health needs such as immunization and chronic disease management. While there is clear promise, the role of SBHCs in preventing/treating childhood obesity has not yet been well investigated.

Providers in SBHCs have the unique ability to access almost the entire adolescent population during a key developmental stage, when youth are beginning to develop autonomy, and are just beginning to make and enact independent health decisions (e.g., what foods to eat, whether/how to exercise). In contrast to their clinical colleagues in the community, SBHC providers have more time to devote to complicated lifestyles and behavioral issues that are often found among adolescents, and which directly influence obesity. This is an exceptionally good fit, as healthy dietary habits are among the top three health topics that adolescents want to discuss with their providers. Particularly within low-income and minority communities, SBHCs may **truly** offer the **only** point of intervention for overweight and obese adolescents.

Need for obesity interventions in high schools: The 2012 Institute of Medicine Report has recommended “making schools a national focal point” in the battle against obesity. The majority of the school-based obesity intervention research has focused on children in middle and elementary schools. However, high school offers an important time to facilitate and foster active living and healthy eating behaviors for adolescents, who are eager to learn skills that directly address their autonomy and independent decision making (such as their choices about health, foods and exercise). This is critically important, as this is the last stage before adolescents enter young adulthood, a time when they are especially vulnerable to weight gain due to leaving home for college, cohabitation, pregnancy, and child rearing. Accessing youth before they become young adults provides a critical time to prevent dramatic increases in the prevalence of overweight and obesity (e.g., from 34% in 12-19 year olds to 62% in 20-39 year olds). Efficacious obesity prevention programs are needed to prepare adolescents for the transition into adulthood.

- ii) Identify specific knowledge gaps which research is intended to fill (rationale for performing the research).

Discussion of school-based BMI screening results: While the Institute of Medicine (IOM) has recommended body mass index (BMI) screening in schools to address pediatric obesity and the US Preventive Task Force

has recently concluded that there is sufficient evidence to support BMI screening in clinical practice, the CDC has maintained that there is insufficient evidence to recommend for or against such programs in the schools. Despite the unclear evidence of school-based BMI screening for obesity prevention, twenty states (40%) have already adopted school-based BMI or body composition screening. Only nine of these states require parental notification and none report directly discussing results with students. Provider discussions about BMI, healthier eating, and physical activity habits is an important missing piece. Not only does it model active collaboration with healthcare providers, it is also consistent with important psychosocial goals for this developmental stage, which include gaining independence from parents and making autonomous decisions. With the use of SBHCs, it is possible to discuss with adolescent students their BMI, diet and physical activity as is recommended in clinical practice.

**Motivational interviewing (MI) to change adolescent eating and physical activity behavior:** While investigations of MI as a prevention/intervention approach for youth at risk for overweight/obesity are still emergent, these studies have strongly indicated the fit and acceptability of MI approaches with minority youth, and among pediatric clinicians. In contrast with the adolescent research, there has been a much broader spectrum of studies with adults, which unequivocally demonstrate that MI contributes to significant changes in physical activity. Specifically, 80% of studies examining MI to increase physical activity demonstrate significant effects. Additionally, naturalistic studies have shown that primary-care physicians are more successful in facilitating activity increases and weight loss among their patients when they are more adherent to MI principles. Furthermore, researchers have explicitly stated that MI would be useful for exercise intervention and prevention efforts with difficult-to-treat conditions like pediatric obesity. However, these recommendations still need empirical evaluation. This study would directly address the paucity of data needed to clarify the efficacy and effectiveness of MI-based interventions to prevent and intervene with adolescent overweight/obesity, with a critical sample of high-risk and high-need adolescents. This evaluation has direct public health implications.

**Referral system to treat students identified with overweight and obesity:** One argument against school-based BMI screening is that there is not an effective referral system in place to link students identified as overweight/obese from the school system to community health resources for treatment. Yet, with SBHCs, it is possible to not only conduct school-based BMI screening, but also to directly treat identified youth. To ensure the efficacy of this mechanism, it is necessary to evaluate the impact of schools with SBHCs as a venue to prevent and treat overweight and obesity for adolescents with limited access to health care. If successful, use of SBHCs may help to decrease the disparity of obesity and metabolic syndrome in adolescent minority populations.

**Use of Adolescents Committed to Improvement of Nutrition and Physical Activity (ACTION) weight management program:** The NHLBI-funded pilot study for this proposal, ACTION (PI: [name]), demonstrated empirical support. More specifically, this program included three primary components: 1) clinical encounters with the SBHC clinician every two to three weeks for a total of eight visits over one academic year, 2) use of MI to support adoption of healthier behaviors, and 3) use of obesity risk reduction strategies from a clinician toolkit co-created with overweight/obese adolescents and their parents. This innovative toolkit includes a DVD (given to the overweight/obese adolescent at the first clinical visit) which was developed with our community adolescent-parent partners and contains: 1) adolescents discussing their motivation for change, 2) strategies targeting energy balance and nutritional quality, and 3) physical aerobic dance (e.g., hip hop, salsa, kick boxing) and strength training exercises created by celebrity fitness trainer [name] (TV fitness host of ESPN International's "Mente y Cuerpo" 2001-2003 and selected top 10 best workout DVD by Fitness Magazine 2006). Print intervention materials in the clinician toolkit include weight loss guidelines, an overview of MI strategies for clinicians, newsletter for caregivers to create a healthier home environment, clinic displays to stimulate discussions about healthier food options, and adolescent session tools (e.g., goal setting, internet resources, and activity/food journal). A Community Based Participatory Research approach was used to ensure that the intervention was culturally- and developmentally-appropriate. In this NIH-funded R21, we also partnered with School Health Advisory Councils (SHACs), comprised of parents, students, community members, and school staff, to demonstrate the acceptability and feasibility of this intervention. Our goal in this pilot R21 was to create an intervention that could be easily implemented across settings with limited resources. Our ACTION weight management program was supported as an innovative solution to this issue, as it is of low-intensity (10-25 hours) and highly feasible and acceptable to our previous school partners. We have not been able to find any published randomized controlled trials evaluating the efficacy of SBHC overweight/obesity

treatment with adolescents. Thus, the proposed study would provide a unique opportunity to evaluate the broader reach and efficacy of this intervention, by evaluating outcomes across a large number of schools with high-risk and high-need youth.

## V. Experimental Design and Methods:

- i) Provide concise description of experimental design and procedures to be used to accomplish study goals. Include precise descriptions of all tests and measurements, and their expected duration. Include optional testing and blinding/un-blinding procedures if applicable.

Research Design: A cluster randomized control trial will be used to test hypotheses. The NM Department of Health, Office of School and Adolescent Health provided a list of recommendations for schools with functioning SBHCs serving a large Hispanic student population. PI [name] successfully approached these schools about collaborating on the proposed research; they agreed (see Letters of Support). To limit the possibility of confounding effects, our collaborating high schools all share the following four characteristics: 1)

Enrollment/ethnicity: At least >700 enrolled students, with at least 40% Hispanic youth, 2) Environmental resources: at least one outdoor field, one gymnasium, and physical activity opportunities, 3) Food service resources: at least one cafeteria, competitive foods (foods brought into schools from outside vendors), and vending machines, and 4) a functioning SBHC. To further control for plausible alternative explanations of outcomes between groups, pretest differences will be compared between groups. The pretests will allow exploration of the possible size and direction of bias that may exist. Thus, the joint use of a pretest and a comparison group will allow examination of possible threats to validity (see Analyses). Assessments will be conducted at pretest (baseline) and annually for two more years (see Table 1). The assessment time waves will allow us to follow 9th grade students annually until their 11th grade year and 10th grade students until their 12th grade year.

Data Collection Measurements: All measures will be collected in both intervention and comparison schools. Protocols with standardized procedures and quality control procedures will be followed by research staff to ensure accuracy, precision, and completeness of data collection. Training for data collection team members will be given by [name], MS (for physical activity related measures) and by [name] (for anthropometrics and nutrition related measures). Each year, before measurements begin, these investigators will retrain and certify the data collection team in all measures. Demographic, physical, dietary intake and physical activity data will

be collected at baseline (pretest), at one year (intermediate), and at 2 years (follow-up) in both intervention and comparison schools. These time intervals will allow us to assess pretest to posttest changes on hypothesized outcomes, and intermediate effects of the intervention. Students will be reimbursed \$20 per measurement wave (total possible=\$60); compensation is consistent with other clinical trials in NM.

- Demographic information to be collected on participants and their parents include age, sex, socioeconomic status, education, and race/ethnicity, using our previously developed Health History Survey. Our Health History Survey also includes questions on family history of type 2 diabetes (first and second degree relatives), chronic medical conditions, and current medications.

A follow-up health history will be administered at intermediate (year one) and follow-up (year two) measurement periods. Participants will update contact and health information. Participants will be excluded at intermediate and follow-up measurement periods if they are pregnant or have been diagnosed with an eating disorder.

- Anthropometric measurements include height, weight, waist circumference and triceps skinfold. Height and weight will be measured twice using the method described by Gordon and colleagues and the National Health and Nutrition Examination Survey (January 2007). Participants will be weighed to the nearest 0.1 kg on a portable strain-gauge digital scale (Seca Model 770) and height will be measured to the nearest 0.1 cm using a vertical measuring rod (Seca Model 213). A third measurement will be done if the first two measurements differ by greater than 0.1 kg (weight) or 0.5 cm (height). If three measurements are taken, the closest two measurements will be used for analysis. BMI will be calculated as kilograms per meters squared. We will use the CDC program, NUTSTAT, that calculates a precise BMI percentile and Z-score based on the participants' height (cm), weight (kg), sex, and age (in months). Participants' waists will be measured twice with a steel tape using the method described by Callaway and the National Health and Nutrition Examination Survey (January

2007). Measurements will be recorded to the nearest 0.1 cm. Triceps skinfold will be measured with the participant in the standing position using a Lange Skinfold caliper (Beta Technology, Santa Cruz, CA). The measurement will be obtained at the upper arm mid-point on the posterior surface of the right upper arm using the technique as described by Harrison and the National Health and Nutrition Examination Survey (January 2007). Three triceps skinfold measurements will be performed and recorded to the nearest 1.0 mm. The average of the three measurements will be used for calculations in determination of percent body fat.

- Blood pressure will be measured on the right arm in the seated position with an aneroid sphygmomanometer. Technique and cuff sizes will be adapted from the National Health and Nutrition Examination Survey (May 2009). Computation of blood pressure percentiles for sex, age and height will follow statistical procedures specified in the Fourth Task Force Report on High Blood Pressure in Children and Adolescents.
- Biomarkers include insulin, glucose, hemoglobin A1c, and lipids will be obtained in overweight/obese adolescents. Samples will be drawn after an ten hour overnight fast. Serum samples will be allowed to clot. All samples will be centrifuged on-site and transported in an ice chest with freezer packs to Tricore Laboratory for processing. Insulin resistance will be calculated using the homeostatic model assessment insulin resistance index [HOMA-IR = (Product of fasting insulin mU/L and fasting glucose mmol/L)/22.5] which has been shown to have reliable sensitivity and specificity in assessing insulin resistance. HOMA-IR increases with increasing insulin resistance.
- Dietary intake will be assessed by the Block Food Screener 2007 a validated food frequency questionnaire. This self-administered tool estimates an individual's usual intake over a period of 1 week. NutritionQuest (Berkeley, CA) will create the data base from the completed surveys for analysis.
- Physical activity will be assessed using the 3-Day Physical Activity Recall (3DPAR) and accelerometry. The 3DPAR has established instrument validity in adolescents based on concurrent observation with motion sensors. Objective assessments of physical activity will be obtained using the ActiGraph GT3X accelerometer (Shalimar, FL). The Actigraph has documented evidence of validity and inter-instrument reliability in children and adolescents. Consistent with previous studies, monitors will be attached to adjustable elastic belts and worn over the right hip during waking hours for 7 consecutive days. Accelerometer counts will be uploaded to a customized EXCEL macro written by [name] for determination of daily time spent in sedentary, light, moderate, vigorous, and moderate-to-vigorous physical activity. The age-specific count thresholds corresponding to these intensity levels will be derived from the MET prediction equation developed by Freedson and co-workers as published by Trost and colleagues and replicate the intensity categories used in population-representative objective monitoring studies (e.g., NHANES).
- We will assess change using readiness to change (casaa.unm.edu), sedentary behavior (Robinson, 1999), eating attitudes (Garner et al, 1982) and health related quality of life (Varni) by evaluating adolescents' status on these measures at assessment waves.
- A questionnaire will be administered to elicit feedback from participants regarding their experiences with the study.

Post-intervention interviews: There is considerable controversy about the psychosocial impact of school-based BMI screening on overweight and obese adolescents. Our experience and formative results from overweight and obese teens in previous studies have been very positive. To contribute to the literature on this topic and improve future dissemination of the proposed intervention, we will conduct a qualitative evaluation of participants' experience with school-based BMI screening and weight management among teens and parents in our intervention. We will conduct 12-20 semi-structured interviews with student participants (3-5 interviews with overweight/obese males, 3-5 interviews with non-overweight/non-obese males, 3-5 interviews with overweight/obese females, and 3-5 interviews with non-overweight/non-obese females). Additionally, 12-20 interviews with parent participants as above will be conducted (3-5 parents of overweight/obese males, 3-5 parents of non-overweight/non-obese males, 3-5 parents of overweight/obese females, and 3-5 parents of non-overweight/non-obese females). The "rule of thumb" most frequently used to determine when a sufficient sample size for interviews has been reached is to conduct interviews until the same perceptions, themes, issues and concerns are emerging from the study participants, called saturation. In our experience saturation occurs between 3-5 interviews of homogeneous informants (i.e., teens of same sex and weight status). Interviews will be semi-structured and last approximately 45 to 60 minutes. Stem questions will focus on student views pertaining to BMI screening and weight management using SBHCs, the processes associated with the proposed

intervention- specifically eliciting perspectives about potential barriers (e.g., social, scheduling) to participation. Parent interviews will triangulate similar issues and also explore barriers/facilitators to supporting interventional goals in the home environment. These interviews will concentrate on process evaluation components aimed at elucidating the contextual factors most influential in participation. SBHC clinicians will provide names of student and parent participants willing to be interviewed; selection will be based on ensuring an equal representation of the two counties where the schools are located. Co-I [name] will train research staff to conduct interviews; she has over 9 years of experience in qualitative research that has been used to develop or modify intervention approaches for youth and underserved communities. Interview questions have been finalized and are titled “parent qualitative questions” and “youth qualitative questions.”

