- Training in and monitoring of MI- All interventionists will be SBHC clinicians from the intervention schools. The goal of MI is to bolster and support youth’s internal motivation, autonomy, and self-efficacy to enact positive behavioral choices, which have been observable up to twelve months post-intervention. In line with the approaches of MI, all interventionists will be taught to utilize MI with adolescents to support and promote the selection of healthier food options and to consistently engage in physical activity for maintenance or achievement of a healthy weight. Consistent with her role across five prior NIH-funded R01s and R03s, Co-I [name] will oversee the training and supervision of MI providers to ensure intervention integrity and fidelity. To that end, all interventionists will be trained using the following five steps. Interventionists will (1) begin their training with an in-person MI training (2 days), which will include interactive training (didactic and role playing) on the use of MI, (2) be required to read the study manuals, (3) pass a knowledge test to evaluate their grasp of the concepts within and behind MI (e.g., with a pass rate of at least 80% on the fidelity checklist and 100% adherence to essential therapeutic elements), (4) watch a MI intervention session with a pilot participant and discuss the details of the session, and (5) conduct two pilot sessions, during which Co-I [name] will evaluate interventionists’ proficiency in MI, with an eye to the following MI integrity components (e.g., MI spirit, MI consistent behaviors including use of reflections, demonstration of accurate empathy, minimal to no closed questions, minimal to no advice without permission). As delineated in the adolescent assent and parent consents, all visits with the adolescent patient will be audio taped to facilitate the continuous monitoring of fidelity of the intervention. All interventionists will participate in once per week teleconference-based supervision, during which randomly selected tapes will be reviewed by [name], who will provide feedback and coaching to the providers. This approach also facilitates continuing performance review, minimization of drift, and a venue to discuss potential problems that might arise in conducting MI-based interventions. We utilize this thorough, multi-level training approach because providers who receive coaching after the initial training are more likely to fully retained clinical trial proficiency levels with MI when compared to those who receive only workshop training.

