Study packets (in both English and Spanish) for enrollment will be sent home with students after a class or assembly presentation. Students will be instructed to review the forms with their parents/guardians in the privacy of their home and to call the study phone number provided in the study packet for questions. Students will be instructed to return completed forms in a sealed envelope (provided by the study team to protect students' privacy) to the SBHC. The SBHC medical assistant will check that consents/assents are completed. UNM research staff will collect the consent/assent forms and call all interested participants and their parents/guardians to ensure that they understand their involvement and expectations of the study. Assent will be reviewed with the student again prior to each measurement wave to ensure they want to continue to participate. This process has been used successfully in our previous studies.

Language about the possible selection to participate in post-intervention interviews will be included in the consent/assent forms as an option that participants can opt in or out of. SBHC clinicians will provide names of student and parent participants willing to be interviewed.

vi) Describe potential risks, including physical, psychological, social, economic, or legal, as well as those that might arise due to a breach of confidentiality.

(1) Identify their seriousness and likelihood.

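### The clinicians who deliver the intervention also supply the names for the Aim 3 interviews, and no sampling rule brings in low attenders or dropouts

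*Combined protocol and SAP*

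**What the plan says.** Section III makes participant feedback a study aim: "Evaluate student and parent feedback at the end of the intervention trial about their experience with school-based BMI screening and weight management". Section V.i, Post-intervention interviews, carries it out by a qualitative evaluation of BMI screening and "weight management among teens and parents in our intervention". The numbers are small: "We will conduct 12-20 semi-structured interviews with student participants", in four sex-by-weight cells of 3-5, and "12-20 interviews with parent participants as above will be conducted". The questions cover views of screening and weight management and, specifically, obstacles to taking part.

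On sampling, the same section says that "SBHC clinicians will provide names of student and parent participants willing to be interviewed", and then that "selection will be based on ensuring an equal representation of the two counties where the schools are located". Under Training in and monitoring of MI, the protocol says: "All interventionists will be SBHC clinicians from the intervention schools".

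Section VI.v says that the possible interview appears on the consent and assent forms "as an option that participants can opt in or out of", and follows this directly with the sentence about clinicians supplying names. It also says that university research staff collect the completed forms. How the opt-in answers and the clinicians' names fit together is not stated.

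**The concern.** The people whose programme is being assessed are the route by which assessors of it are found. No bad intent is needed for this to matter. ACTION is planned as 16 sessions over two years (Treatment intervention), with a telephone call to the caregiver after each visit. A student who stops coming has little further contact with the clinician, and that student's parent gets fewer calls. The families who know most about barriers are the ones the clinician is least likely to have in mind.

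The stopping rule could hide the gap. The plan expects saturation after 3-5 interviews with similar informants. If mostly engaged participants are named, their accounts may agree early and saturation may seem to have been reached before any dropout has been heard.

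At stake is the credibility of Aim 3: its evidence on barriers, its contribution to the debate about the psychosocial effect of school BMI screening, and its use in planning dissemination. Attrition is a live issue in this trial, because the sample size section raises enrolment by 5% after first-year losses exceeded expectation.

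**Working it through.** **Who names, who delivers, what limits the choice.**
- Names come from SBHC clinicians (V.i and VI.v).
- Delivery is by SBHC clinicians of the intervention schools (V.i, Training in and monitoring of MI).
- Interviewees come from the intervention (V.i, Post-intervention interviews).
- The stated controls are sex, weight status and county. Neither attendance nor dropout is among them.
- Willingness is also recorded on forms that research staff collect (VI.v).
- ACTION attendance is tracked (V.iii, Process measures and analysis), so a control on engagement is feasible.

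**The plan's own figure.** Four cells of 3-5 give 4 × 3 = 12 and 4 × 5 = 20. The stated 12-20 reproduces.

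**Scale.** The interviews follow the intervention, so the relevant denominator is students after attrition. The inputs are 480 intervention students (VI.ii), or 1008 / 2 = 504 if the enlarged sample is split equally (an assumption), and 35% planned attrition (V.iii).
- 480 × 0.65 = 312, and 504 × 0.65 = 327.6, about 328.
- 12/312 = 3.8% and 20/312 = 6.4%.
- 12/328 = 3.7% and 20/328 = 6.1%.

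So about 4-6% of retained intervention students are interviewed. For the overweight/obese cells, the plan's 224 retained students give 224 / 2 = 112 in the intervention arm. The 6-10 interviews there are 6/112 = 5.4% to 10/112 = 8.9%. These fractions show how much room there is in who gets named. They do not measure the adequacy of a qualitative sample.

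**Illustration with assumed values.** Let q be the share of overweight/obese intervention students with low engagement, and r the odds that such a student is named relative to an engaged one. Neither is in the documents. The share of low-engagement students among those named is s = qr / (qr + 1 − q), and the chance that n interviews include none is (1 − s)^n. With q = 0.30:

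| r | s | none in 6 | none in 10 |
|---|---|---|---|
| 1 (no preference) | 0.300 | 12% | 3% |
| 0.5 | 0.176 | 31% | 14% |
| 0.25 | 0.097 | 54% | 36% |

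For q from 0.20 to 0.50 and n = 10, the chance of none runs from 11% down to under 1% at r = 1, and from 55% down to 11% at r = 0.25. A moderate preference in naming could thus leave this group unheard, but the result depends on q and r.

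**The case against.** The plan says that clinicians provide names of willing participants. It does not say that they may hold any back, and selection is a separate clause with its own county rule. Signed forms are returned to the SBHC, so the clinicians might simply pass on who opted in. The opt-in is given at enrolment and the interviews come after two years, so someone has to check willingness again.

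There are also safeguards. Research staff conduct the interviews. Parents are interviewed separately from students and serve as a cross-check. A feedback questionnaire goes to participants. Eating attitudes and quality of life are measured at the assessment waves, and adverse events are monitored. Two of the four student cells hold students below the 85th percentile, who have only the annual discussion, so the dropout mechanism applies mainly to the ACTION cells. Purposive sampling is sound practice in qualitative work, and random draws within cells of 3-5 would be a preference, not a requirement.

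Much of this stands, and it limits the claim. A reader might infer that clinicians will screen out critics, that the Aim 3 sample is in fact biased, or that it cannot reveal barriers or harms. The documents support none of these. A reader might also infer that a compiled list of volunteers exists and makes the clinicians unnecessary, but Section VI.v describes only an option on a form.

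What does not stand is the suggestion that the safeguards close the gap. An independent interviewer cannot hear someone who was never named, and parents are named by the same route. The questionnaire reaches participants directly, but the analysis section for Aim 3 covers only the interviews. The sampling is purposive on sex, weight and county, and not on engagement, which is what a question about barriers most needs.

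**Conclusion.** The point holds as a risk. Aim 3 may under-represent disengaged or dissatisfied participants, chiefly overweight/obese students offered ACTION and their parents, because the providers supply the names and no rule secures low attenders or dropouts. The size of any bias cannot be obtained from the documents, and its direction is inferred from who stays in contact with the clinicians. The 4-6% sampling fraction rests on the planned 35% attrition and an equal split between arms.

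The effect is confined to Aim 3. Hypotheses 1a, 1b and 2 do not use the interviews. The correction is worth making because it is cheap and improves the evidence for a stated aim.

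**What to change.** Replace the sentence on clinicians supplying names, in Section V.i (Post-intervention interviews) and Section VI.v, so that:

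1. Research staff identify interviewees from the consent and assent opt-ins and reconfirm willingness at the time of interview.
2. Selection stays within the existing sex-by-weight cells and two counties.
3. Some places in the overweight/obese cells go purposively to students with low ACTION attendance or who discontinued it, and to parents of such students, using the attendance already tracked. Only those whose agreement to be contacted still stands are approached.
4. The report gives the numbers approached, refused and interviewed, by cell.

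The cost is a wording change and modest extra effort to reach low attenders. The 12-20 student and 12-20 parent interviews can stay as planned. Cells will be somewhat less homogeneous, so saturation may come nearer the upper end of 3-5. Those who opted in are still self-selected, so the change reduces the bias without removing it.
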